If LMP is uncertain or unknown, the ultrasound-established gestational age estimation will be used to establish the gestational age of the pregnancy.

(d) Gestational Age Dating When the LMP is Uncertain or Unknown AND No Prior First or Second Trimester Ultrasound Has Been Performed:

An ultrasound performed at screening, within the second trimester ($\leq 27^{6/7}$ weeks) will be used to establish the gestational age.

3) Documentation of a second or third (between $18^{0/7}$ weeks and prior to randomization) trimester ultrasound with no major fetal anomalies identified.

4) Good general maternal health as demonstrated by:

- Medical history (including history of clinically significant adverse reactions to prior vaccines and allergies).
- Physical examination including at least vital signs (blood pressure, pulse, respirations, and axillary body temperature); weight; height; examination of the HEENT, cardiovascular, pulmonary, gastrointestinal (abdominal), musculoskeletal, lymphatic, and dermatologic organ systems; and documentation of fetal heart tones. Note that abnormal vital signs may be repeated at the investigator's discretion since these measures may be labile. Vital signs should be assessed in the context of normal values for the third trimester of pregnancy (see the **Study Operations Manual**).
- Clinical laboratory parameters that include:
 - For the first year of study conduct in any country, normal/clinically insignificant blood urea nitrogen (BUN), creatinine, alanine aminotransferase (ALT), aspartate aminotransferase (AST), total bilirubin, alkaline phosphatase (ALP), hemoglobin, white blood count, and platelet count. Note that normal ranges for clinical laboratory parameters will be based on reference ranges appropriate for the third trimester of pregnancy, specified in the toxicity grading scale (TGS, provided in the **Study Operations Manual**) and should be referenced to assess for any abnormalities. This testing should be performed by the central laboratory.
 - For all subjects, serologic exclusion of infection with hepatitis B (HBV) and C (HCV) viruses, syphilis and HIV as documented by testing (performed at the central or local laboratory) at screening or by medical records during the current pregnancy.

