7.1 Clinical Laboratory Testing

The following laboratory tests will be performed by a qualified central laboratory (unless otherwise stated) designated by Novavax on blood samples collected from maternal subjects enrolled in the first year of study conduct in any country at the screening visit (Days -28 to 0) and on Day 14 (unless the subject delivers prior to this visit at which time the blood sample will be obtained at delivery):

- Serum chemistry – alanine aminotransferase (ALT), aspartate aminotransferase (AST), total bilirubin, alkaline phosphatase (ALP), creatinine, and blood urea nitrogen (BUN).
- Hematology – hemoglobin, platelet count, and white blood cell (WBC) count.

Additional clinical laboratory antigen tests/serologies for HIV, syphilis, HBV, and HCV detection will be performed by a central or local laboratory at the screening visit, if results are not available in prior data collected during the course of the current pregnancy.

A urine pregnancy test will be administered to all maternal subjects at the D+180 visit; a positive result will trigger additional follow-up to determine the outcome of the pregnancy.

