Appendix 1 – RSV-M-301 Study Procedures Schedule

Maternal Subject Study Procedures

Study Day:	-28 to 0	0	0-6	7 ^[1]	14 ^[1]	28 ^[1]	Delivery	D+35 ^[1]	D+180 ^[1]
Window (days):	--	--	--	+2	±2	±2	--	±7	±14
Approximate Week of Gestation:	24-36 ^{0/7}	28-36 ^{0/7}	28-36	29-37	30-38	32-40	--	--	--
Informed consent	x								
Medical history	x								
Physical exam	x								
Vital signs	x	x ^[5]		x	x		x ^[10]	x	x
Physical exam, if indicated		x		x	x		x	x	x
Ultrasound	x ^[2]								
Clinical safety phlebotomy	x ^[3]				x ^[3]		x ^[11]		
HIV, syphilis, HBV, and HCV testing (if applicable)	x ^[4]								
Pregnancy test									x
Fetal heart tones	x	x ^[5]		x	x				
Confirm eligibility		x							
Injection with recommended licensed vaccine dose	x ^[6]								
Injection with RSV F vaccine or placebo		x							
Diary card completed			x						
Diary card reviewed and collected				x					
Distribution of Study Identification Card ^[9]		x		x	x	x	x	x	
Memory aid distribution				x					
RSV serology phlebotomy	x				x		x ^[7]	x	x
Cord blood							x ^[8]		
RSV surveillance						Continuous			

Maternal Subject Study Procedures

Study Day:	-28 to 0	0	0-6	7^[1]	14^[1]	28^[1]	Delivery	D+35^[1]	D+180^[1]
Window (days):	--	--	--	+2	±2	±2	--	±7	±14
Approximate Week of Gestation:	24-36^{0/7}	28-36^{0/7}	28-36	29-37	30-38	32-40	--	--	--
AEs, MAEs, SNMCs, and SAEs query	x	x		x	x	x	x	x	x
Concomitant medications		x		x	x	x	x	x	x
Document perinatal management & GBS screening/treatment results	x						x		

- [1] Performed as a telephone or SMS contact visit (Day 28 only) using an IRB/IEC-approved script, if applicable, or as an in-clinic or home visit (Day 7, Day 14, D+35, and D+180) to monitor for safety. Depending on responses, maternal subjects participating via telephone or SMS contact or home visit, may be asked to return to the clinic or to schedule a home visit for further evaluation.
- [2] May be performed if subject does not have a prior second or third-trimester ultrasound that indicates there are no fetal anomalies.
- [3] To be performed at least two days prior to the planned Day 0 vaccination and on Day 14 in all subjects enrolled in the first year of study conduct in any country for serum chemistry (ALT, AST, total bilirubin, ALP, creatinine, and BUN) and hematology (hemoglobin, platelet count, and WBC count) assessments.

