Healthy women in the third trimester of a singleton uncomplicated pregnancy, at low risk of obstetrical complications, and ≥ 18 to ≤ 40 years of age (lower limit of 18 years and 0 days and an upper limit of 40 years and 0 days) will be enrolled and randomized initially in a 1:1 ratio, into one of two treatment groups, active or placebo, over approximately the 3 months prior to peak RSV season, as shown in [Table 1](#). After the first global season of enrollment, the randomization scheme will be changed from a 1:1 (active:placebo) ratio to a 2:1 (active : placebo) ratio to enable more efficient accrual of the safety database. Due to the importance of infant RSV exposure in order to demonstrate efficacy of the maternal immunization strategy, investigators will be instructed to base maternal enrollment on a projected date of delivery for each maternal subject. The estimated date of the earliest delivery (EDD-E) will be approximately 6 weeks prior to the historic average onset date of increased RSV transmission at each study site. The estimated date of the latest delivery (EDD-L) will be calculated based

on the historic average end date of RSV transmission at each study site, such that participating infants are likely to have a minimum 3 month exposure to RSV transmission. The Sponsor will assist and provide guidance to each site in determining the EDD-E and EDD-L using best available site-specific, local, state/provincial, or national surveillance data to the extent available. The trial will begin with enrollment of women in the Northern hemisphere, followed by enrollment in the Southern hemisphere for the first global RSV season.

Table 1: Treatment Assignments

Treatment Group	Target Maternal Subjects/Group ^[1]	Test Article	Dosing Volume	Vaccination Day
A	~1562	Saline placebo	0.5 mL	Day 0
B	~3038	RSV F vaccine		

^[1] The target number of subjects that may be enrolled over multiple global RSV seasons, based on a 1:1 randomization for the first season and 2:1 (active / placebo) randomization for all subsequent seasons.

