12.1. Overall Handling of Adverse Events

The principal variable for evaluation of the safety profile for the RSV F vaccine will be the number and percentage (95% CI) of maternal subjects with solicited and unsolicited adverse events (including MAEs and SAEs) recorded post-vaccination, and the number and percentage (95% CI) of infants with unsolicited AEs occurring since birth. An overall summary will present the number and percentage of solicited adverse events in maternal subjects by verbatim term and treatment group; and unsolicited adverse events by MedDRA SOC and PT, and by treatment group for all maternal and infant subjects in the Safety Population. Laboratory values and vital signs will also be summarized (percentages) by treatment group for all maternal subjects in the Safety Population.

Solicited adverse events occurring in the first 7 days after each dose of test article will be presumed to be related; and severity will be graded by specific definitions included in the protocol and subject diary. Unsolicited adverse event summaries by relationship to study vaccine will be categorized as “not related” (including “unrelated or unlikely”) or “related” (including “possible, probable, and definite”). For multiple occurrences of an adverse event in the same subject, a subject will be counted only once, using the most severe or most related occurrence for the summarization by severity or relationship to study vaccine, respectively.

Solicited adverse events will not be coded, and will be summarized by solicited term only. All unsolicited adverse events will be coded using MedDRA version 16.1.

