12.2. Analyses of Safety Objectives

Safety will be summarized for maternal and infant subjects separately. Safety will be summarized overall and by treatment group for maternal and infant subjects based on percentages.

Tabulations of counts and proportions of the following safety parameters, by treatment group and overall, will be produced for maternal subjects:

- Solicited seven-day reactogenicity events by severity;
- Clinical laboratory safety abnormalities by severity;
- Caesarean, vaginal, and instrument-assisted vaginal modes of delivery;
- Pre-specified third-trimester pregnancy and delivery complications (i.e., stillbirth, placental abruption, preterm birth, preterm premature rupture of membranes, hypertensive disorders of pregnancy, third-trimester hemorrhage, and gestational diabetes), and labor and delivery complications (i.e., emergency Caesarean section, postpartum hemorrhage, chorioamnionitis, and maternal fever or infection); and
- Unsolicited adverse events through 180 days post-delivery by severity and relatedness (possibly, probably, or definitely), including SAEs, MAEs, and SNMCs.

Tabulations of counts and proportions of the following safety parameters, by treatment group and overall, will be produced for infant subjects:

- Congenital anomalies; respiratory failure other than RSV-associated hospitalization; neonatal death; infant death; sudden infant death syndrome; asphyxia; neonatal or hypoxic-ischemic encephalopathy; or other adverse events or complications of adverse events that necessitate hospitalization during the neonatal period and through the first year of life;
- All other unsolicited/unspecified adverse events by severity, relatedness, and seriousness, including respiratory events that test negative for RSV by RT-PCR.

Summary statistics will also be provided for infant length, weight, FOC, 1- and 5-minute APGAR scores, and responses to environmental and behavioral queries, through one year post-delivery overall, and by treatment group. Results of developmental testing will be summarized by treatment group, and percentages of infants in the developmental testing subset above normal, normal, at-risk at 6 or 12 months, and at-risk at both 6 and 12 months.

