12.9. Laboratory Data

Descriptive statistics (mean, median, standard deviation, minimum and maximum values) for continuous laboratory parameters and/or number (percentage) for categorical laboratory parameters will be presented by treatment group. Change from pre-vaccination (Day 0) to Day 14 post-vaccination will also be presented for all continuous parameters.

All laboratory values will be presented in subject data listings, including any available drug screen parameters, and additional labs ordered by the investigator, if applicable. The following protocol-specified parameters (see protocol, Section 7) will be included in summary tables:

- Hematology
 - White Blood Cell count [w/differential] ($\times 10^9/\text{L}$).
 - Hemoglobin ($\times 10^{12}/\text{L}$).
 - Platelet count ($\times 10^9/\text{L}$).
- Serum Chemistry
 - Serum creatinine ($\mu\text{mol}/\text{L}$).
 - Alkaline phosphatase [ALP] (U/L).
 - Alanine aminotransferase [ALT] (U/L).
 - Aspartate aminotransferase [AST] (U/L).
 - Blood urea nitrogen [BUN] (mmol/L).
 - Total bilirubin ($\mu\text{mol}/\text{L}$).
- HIV, HCB, and HCV antigen tests/serologies as required.

A listing of subjects with laboratory values recorded as newly abnormal following study vaccination and meeting toxicity mild criteria (Grade 2) or above as specified in the TGS for the study, will be presented at Screening and Day 14 for clinical laboratory data. If the number of events warrants, a tabular summary (number and percentage of abnormal laboratory values per TGS criteria) of these data will be included. Tabular summaries by race/ethnicity, nationality or geography, or other demographic features may be created.

Toxicity grade shift summaries by treatment group will be generated for each parameter. A shift table of the change from Screening to Day 14 in toxicity grade rating time-points labeled as “Decrease by 2 grades”, “Decrease by 1 grade”, “Normal” (or “No Change”), “Increase by 1 grade”, “Increase by 2 grades”, etc., will be presented as number (percentage) of total subjects by treatment group. Each of these categories will only be presented when data are available.

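### The laboratory shift table takes its percentages over total subjects, although safety bloods are planned only for women enrolled in their country's first year, so its rates are diluted

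*SAP*

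**What the plan says.** Laboratory testing is restricted by calendar. Protocol 7.1 plans chemistry and hematology at Screening and Day 14 on "blood samples collected from maternal subjects enrolled in the first year of study conduct in any country". The schedule in Protocol Appendix 1 repeats this ("on Day 14 in all subjects enrolled in the first year of study conduct in any country"), and inclusion criterion 4 in Protocol 5.1 opens its laboratory requirement with "For the first year of study conduct in any country, normal/clinically insignificant blood urea nitrogen (BUN)". Protocol 6.1.1.2 gives women enrolled in any later year only the infection serologies.

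The SAP does not carry this restriction into its denominators.
- SAP 12.9: the change in toxicity grade from Screening to Day 14 "will be presented as number (percentage) of total subjects by treatment group".
- SAP 12.1: "Laboratory values and vital signs will also be summarized (percentages) by treatment group for all maternal subjects in the Safety Population". SAP 5.1 defines that population as every woman who received test article.
- SAP 12.2 lists "Clinical laboratory safety abnormalities by severity" among the maternal tabulations and names no denominator.
- SAP 16 asks for a missing-data category in categorical tables.

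Allocation also changed over time (SAP 2): "After the first global season of enrollment, the randomization scheme will be changed from a 1:1 (active:placebo) ratio to a 2:1".

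**The concern.** A woman with no planned safety bloods cannot show a grade shift. If she stays in the denominator, the printed percentage is no longer the rate among women who were observed. Laboratory assessment is a listed maternal safety endpoint (SAP 4.3.2), and a reader of the table would take the percentages as rates of laboratory abnormality.

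The dilution also need not be equal between arms. Women without planned bloods come from after the first global season, when two were allocated to vaccine for each one to placebo. They therefore make up a larger share of the vaccine arm, and equal true rates would print slightly lower for vaccine than for placebo.

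**Working it through.** **Inputs**
- Arm targets: 3,038 vaccine and 1,562 placebo, 4,600 in total (SAP Table 1 and SAP 13).
- Projected global season 1: 20 + 154 = 174 women. Projected season 2: 210 + 1,094 = 1,304 (SAP Appendix 1, section 6.1, base accrual row).
- Allocation: 1:1 in global season 1, then 2:1 (SAP 2).
- L, the number of women enrolled after season 1 but still in their country's first year: not given. It is an assumption, varied from 0 to 4,600 − 174 = 4,426.
- Season 1 women are all taken to be in a first country year, and every woman with planned bloods is taken to have both results.
- True shift rate: 10% in both arms, for illustration. It cancels from the ratio.

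**Reproducing the arm targets**
- Vaccine: 174/2 + (2/3) × 4,426 = 3,037.7, against a stated ~3,038.
- Placebo: 174/2 + (1/3) × 4,426 = 1,562.3, against a stated ~1,562.

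**Tested fraction and printed rate**
- Vaccine fraction = (87 + 2L/3) / 3,038.
- Placebo fraction = (87 + L/3) / 1,562.
- Printed rate = true rate × tested fraction.

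| L | Tested, vaccine | Tested, placebo | 10% prints as (vaccine v placebo) | Apparent ratio |
|---|---|---|---|---|
| 0 (season 1 only) | 2.9% | 5.6% | 0.29% v 0.56% | 0.51 |
| 652 (plus half of season 2) | 17.2% | 19.5% | 1.72% v 1.95% | 0.88 |
| 1,304 (plus all of season 2) | 31.5% | 33.4% | 3.15% v 3.34% | 0.94 |
| 2,000 | 46.8% | 48.3% | 4.68% v 4.83% | 0.97 |
| 3,000 | 68.7% | 69.6% | 6.87% v 6.96% | 0.99 |
| 4,426 (everyone) | 100% | 100% | 10% v 10% | 1.00 |

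**Gap between arms**
- At L = 0 the gap in coverage is 5.57% − 2.86% = 2.7 percentage points.
- It shrinks in proportion to (1 − L/4,426), so 2.7 points is the maximum.

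**If 1:1 applied only to the first northern season**
SAP Appendix 1, section 1.0, says this, which makes it 20 women.
- Arms: 10 + (2/3) × 4,580 = 3,063 vaccine and 10 + (1/3) × 4,580 = 1,537 placebo. These fit Table 1 less well.
- With season 1 alone tested, 154 of its women fall in the 2:1 period. Coverage is (10 + 102.7)/3,063 = 3.7% against (10 + 51.3)/1,537 = 4.0%, a ratio of 0.92.
- The direction is the same and the gap is smaller. The overall dilution is essentially unchanged.

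**With paired results as the denominator**
Both arms print 10% for every L, a ratio of 1.00.

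**The case against.** SAP 12.9 does not define total subjects. A shift can be computed only for a woman with both grades, and 12.9 adds that shift categories appear only where there are data, so a programmer might use paired results anyway. That reading is possible. It runs against 12.1, which points to the whole Safety Population, and against the missing-data category in SAP 16, which fits a whole-arm denominator. Where the SAP wants a subset it says so, as 12.2 does for developmental testing. The sentence about categories decides which rows print, not what they are divided by.

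A missing-data row would let a careful reader recover the tested-subset rates. That also stands, but the row discloses the problem without correcting the printed percentages.

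Three stronger readings are tempting and are not supported:
- *Untested women are counted as normal.* SAP 12.9 has a row for no change, and nothing assigns untested women to it.
- *Every laboratory rate is diluted.* The quoted denominator governs only the shift table. Means and changes from baseline are untouched. The optional summary of abnormal values is a percentage of values, and newly abnormal Grade 2 or higher, Grade 3 and AE-associated values are listed individually.
- *The table would halve the apparent vaccine risk.* The ratio of 0.51 needs no country to have opened after season 1. The change history in Protocol Appendix 5 does not date country openings, but it cites regulators for Chile and New Zealand at version 8.0 and adds regional background for India, Southeast Asia and the Philippines at version 9.0. That makes 0.51 a poor lead scenario.

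**Conclusion.** Wrong as written, in a descriptive safety table only. Under the denominator that 12.9 and 12.1 indicate, each shift-table percentage is understated by the untested fraction of its arm. If all of projected seasons 1 and 2 were tested, the table would show about one third of the true rate. The factor cannot be fixed more closely, because the number tested is not in the documents and the season sizes are projections.

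The difference between arms is real in direction whenever some later women went untested, but it is secondary: an apparent ratio of 0.94 if all of season 2 was tested, closer to 1 with more, and closer still if 1:1 covered only the first northern season. No formal test is planned on this table, and efficacy conclusions are not touched.

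**What to change.** In SAP 12.9, replace the reference to total subjects with: *of subjects with both a Screening and a Day 14 result for that parameter*. For the laboratory-abnormality table in 12.2, state that the denominator is subjects with a post-vaccination result. Print the number tested per arm in the column headers of both.

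First-year women who deliver before Day 14 have their safety bloods drawn at delivery instead (Protocol 6.1.1.5 and 7.1). Show those results separately; whether to pool them with Day 14 is a different choice, and the shift table does not provide for it.

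The cost is SAP wording and table shells. No new data are needed. The printed abnormality rates will be higher, because they will be rates among women who were tested.

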13. SAMPLE SIZE CONSIDERATIONS

This study is designed to enroll approximately 4,600 total maternal subjects that include a minimum of 3,000 RSV F vaccine recipients over 4 global RSV seasons.

Assuming a medically-significant RSV LRTI incident rate of 4% in the placebo group and a vaccine efficacy of 65%, then the power of the design to claim success is 87%. [Table 3](#) summarizes the power for different placebo attack rates and vaccine efficacies. Power calculations were performed using the normal approximation (NCSS PASS 14). An estimated PP population size of 4,218 total evaluable infant subjects (2,786 in the RSV F vaccine group and 1,432 in the placebo group to account for 1:1 and 2:1 randomization ratios in Year 1 and the subsequent years, respectively) was used for all calculations.

The target sample size of the safety and efficacy database in third-trimester pregnancy that will be required for licensure is at least 3,000 actively-immunized maternal subjects and their infants. Therefore, the final analysis for efficacy will commence only after a total of 3,000 subjects have been enrolled in the active treatment arm. If no events of a given class are observed among the 3,000 subjects receiving the RSV F vaccine, an approximation to the one-sided upper 95% confidence bound on the rate of SAE occurrence would be 0.1%.

Table 3: Power Calculations for the Primary Efficacy Endpoint (Medically-Significant RSV LRTI Through 90 Days)

Placebo Event Rate	True Event Ratio	Efficacy (1-RR)	Power ^[1]
0.02	0.5	50%	17%
	0.4	60%	41%
	0.35	65%	57%
	0.3	70%	72%
	0.2	80%	92%
0.03	0.5	50%	26%
	0.4	60%	59%
	0.35	65%	76%
	0.3	70%	88%
	0.2	80%	99%
0.04	0.5	50%	34%
	0.4	60%	73%
	0.35	65%	87%
	0.3	70%	96%

Table 3: Power Calculations for the Primary Efficacy Endpoint (Medically-Significant RSV LRTI Through 90 Days)

Placebo Event Rate	True Event Ratio	Efficacy (1-RR)	Power ^[1]
0.05	0.2	80%	>99%
	0.5	50%	42%
	0.4	60%	83%
	0.35	65%	94%
	0.3	70%	99%
	0.2	80%	>99%
0.06	0.5	50%	50%
	0.4	60%	90%
	0.35	65%	97%
	0.3	70%	>99%
	0.2	80%	>99%

^[1] Estimated using normal approximation to rule out H0: Vaccine Efficacy < 30% using one-sided Type I error rate of 0.0124.

